In the reading span, participants read a series of either semantically congruent sentences or syntactic prose sentences (e.g., As the ship gets better, your child needs to develop this oven) for which they make sentence acceptability judgments on each sentence. Participants make an acceptability judgment by pressing a Yes button or No button at the bottom of the screen. Once participants make a decision, the sentence disappears, and participants are presented with accuracy feedback. At the end of the set, participants are cued to recall the last word of each sentence in the order in which they were presented. The cued recall screen consisted of a set of empty text boxes that participants can press and then type their responses via an on-screen keyboard, with no time limit. Acceptable sentences are adapted from two sources. The Nelson and Narens (1980) general information question norms provided 244 sentences. The other source was the Manually Annotated Sub-Corpus (MASC) of the Open American National Corpus (Ide et al., 2013), which provided 301 sentences that ranged widely in topic, length, and syntactic structure. In addition, 346 unacceptable sentences were adapted from the syntactic prose conditions in earlier studies by Lee and Federmeier (2011) and Payne et al. (2015). Unacceptable sentences have syntactically well-formed sentence frames, but contain no coherent message-level semantics. All sentences ranged between 60 and 90 characters, and all sentence final words were between 4 and 9 characters.

In the lexical decision span task, participants are presented with a set of letter strings constituting words (e.g., seek) or non-words (e.g., ceek) and are cued to decide whether or not each string formed a word or not. The letter strings are presented for 4 s. At any point within this interval, participants decide if

the letter string was a word or non-word by pressing a Yes button or No button at the bottom of the screen. Once participants make a decision, the letter string disappears, and participants are presented with accuracy feedback. Following each lexical decision, an unrelated single letter is presented for 1500 ms for participants to recall at the end of the set. At the end of each set, participants are cued to recall each of the letters in the order in which they were presented. The cued recall screen consists of a set of empty text boxes that participants can press and then type their responses via an on-screen keyboard. Participants have no time limit to enter their recall responses at the prompt. A total of 9,000 common and proper nouns and 10,000 phonologically regular and pronounceable non-words were generated from the English Lexicon Project database (Balota et al., 2007). Word/non- word strings ranged in length between 4 and 9 characters (for word stimuli: log word frequency range: 5 to 13.67).

In the category span, participants are presented with a semantic category at the top of the screen (e.g., weather) along with a set of single words for which they made validity judgments (e.g., humidity - Yes; chocolate - No). Each trial consisted of the category and target word presented for 4 s. At any point within this duration, participants can decide if the target matches or does not match the category by pressing a Yes button or No button at the bottom of the screen. Once a participant makes a decision, the target word disappears and s/he presented with accuracy feedback. The program would then progress to the next trial within the set. At the end of each set, participants are cued to recall each of the words in the order in which they were presented. The cued recall screen consists of a set of empty text boxes that participants can press and then type their responses via an on-screen keyboard. Participants have no time limit to enter their recall responses at the prompt. Categories and exemplars were drawn from the Van Overschelde et al. (2004) category norms. The final stimulus set contains a total of 69 unique categories and over 1500 unique words. Items were drawn randomly such that, within a set, each word had an equal probability of belonging to the presented category or not. Across training sessions, items were rotated through such that all categories had to be selected at least once before a particular category could be repeated again.

In the placebo control, participants engaged with a speeded lexical decision task. This was an active control matched to the other conditions in materials and engagement (speed increased and decreased adaptively to performance) but without the memory component.

Electronic tablets were delivered to the participants' homes along with detailed instructions and a log book, using contact-free delivery during the COVID-19 pandemic. Participants kept an iPad for each phase of training for about two weeks and could complete their 10 sessions of training on any days during the two weeks.

The pre- (administered Prior to Phase 1) and posttest (administered after Phase 2) batteries were programmed in Qualtrics and administered online. The testing session began with the experimenter on the phone to consent the participant and provide guidance in initiating the protocol. The experimenter was available by phone throughout to answer any questions throughout the session. The testing session generally required 1.5-2 hours. To the extent possible, the pretest-posttest interval was held constant ( $M = 34.5$  days,  $SD = 7.0$ ). There were no differences among the groups,  $F < 1$ .

Outcome measures included rate of learning during Phase 2 and change in cognitive measures from pre- to posttest.

### ***Statistical Analysis Plan***

The primary outcomes were (a) standard unit change in cognitive measures from pre- to posttest (i.e., posttest score - pretest score) / standard deviation at pretest) for reading span and a composite of work and (b) daily mean reading span score achieved across the 10 days of training in Phase 2. For the latter variable, calculations were based on scores from Trial 2 to the end of the training block (we discarded Trial 1 because this trial only included one element to remember and thus, elicited uniform performance across participants). Pre- to posttest change was analyzed using one-way ANOVA to test differences among the four groups with post hoc Bonferroni comparisons to correct for the number of

comparisons. Acquisition of the reading span in Phase 2 (change across the 10 days of practice) was analyzed with mixed-effects linear regression using the lme4 and lmerTest packages for R version 4.2.2 (R Core Team, 2022). The PC Group was set as reference in comparisons with other groups in an analysis with Training Day and Phase 1 Training Group as the fixed factors, and by-subject random intercept, using the restricted maximum likelihood (REML) method of estimation. The design was powered at .9 to detect an effect size of .43 for differences between the groups with an alpha of .05, and to detect an effect size of .14 for group differences in change across 10 days (Faul et al., 2007), though of course, there estimates of power for linear mixed-effects models are controversial. There was no correction for the number of tests in this latter analysis.

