To this end, participants engaged in two phases of training. The target task in Phase 2 was the complex reading span, which has been found to be predictive of standardized tests of verbal ability and measures of language comprehension (Baddeley, 2012; Daneman & Carpenter, 1980; Daneman & Merikle, 1996; Payne & Stine-Morrow, 2017; Peng et al., 2022; Stine & Wingfield, 1987). As a WM task, the reading span requires the concurrent management of sentence processing and a memory load. Participants were randomly assigned to one of four groups that varied in the type of training in Phase 1. In the Different Mixed (DM) condition, participants practiced lexical decision span and category span tasks, two different tasks similar to the reading span in requiring the individual to manage a memory load while processing verbal material but with different sorts of processing components. In the Different Single (DS) condition, participants practiced only the lexical decision span, which provided less diverse experience with tasks that depend on WM. These were contrasted with two controls, a Same Task (ST) condition in which participants practiced the reading span, exactly the same as the target task, and a Placebo Control (PC) condition, in which participants made speeded judgments to the same verbal stimuli as in the lexical decision task but with no memory component, and hence, no demand to simultaneously manage processing and memory (i.e., WM). We measured both how quickly the target task in Phase 2 was acquired, as well as pre- to posttest change in practiced and unpracticed WM tasks and episodic memory tasks, as a function of prior experience in Phase 1.

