According to the Principle of Direct Transfer, training in the reading span in Phase 2 should be accelerated by conditions in Phase 1 that share the most elements with Phase 2 training. Thus, Principle of Direct Transfer predicts an early advantage for the ST group relative to the other three groups that would be sustained through acquisition, as well as some advantage for the two other WM training groups, the DM and DS conditions, relative to the PC condition. The Principle of Mutualism, on the other hand, predicts accelerated acquisition for the DS, and especially the DM, conditions, relative to the PC condition, on par with the ST condition. This is because even though the DS and DM tasks share fewer elements with the target task, the Mutualism principle predicts that the acquisition of the elements that are shared enhances plasticity of the unpracticed elements of the target task. Critically, Mutualism would predict that any advantage of the DS and DM conditions would not be immediately apparent but only emerge with practice.

The two theories also make contrasting predictions for pre- to posttest change. Principle of Direct Transfer would predict greater change in the practiced WM tasks relative to the unpracticed WM tasks for the ST, DS, and DM groups relative to the PC control. Specifically, the ST group — who exclusively practiced the reading span (RS) task in both phases of training would be expected to show the greatest

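### Pre-to-post change, a primary outcome, is tested by one-way ANOVA with no pretest covariate: valid, but it gives up precision unless the pretest slope is at or near 1

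*Combined protocol and SAP*

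**What the plan says.** The Statistical Analysis Plan names two primary outcomes. The first is "standard unit change in cognitive measures from pre- to posttest (i.e., posttest score - pretest score) / standard deviation at pretest". Its analysis is given in one sentence: "Pre- to posttest change was analyzed using one-way ANOVA to test differences among the four groups", with Bonferroni post hoc comparisons. No covariate is named for this analysis, and nothing in the Study Protocol adds one.

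Two facts in the Study Protocol make the pretest a proper baseline covariate. Under Objectives, "Participants were randomly assigned to one of four groups that varied in the type of training in Phase 1". Under Methods, "The pre- (administered Prior to Phase 1) and posttest (administered after Phase 2) batteries were programmed in Qualtrics". The pretest is therefore measured before the groups diverge, and it is already held for everyone with a change score.

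On power, the plan says: "The design was powered at .9 to detect an effect size of .43 for differences between the groups", at alpha .05. It does not name the effect-size metric, and it gives no sample size, pre-post correlation or SDs.

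**The concern.** A change score subtracts the whole of the pretest from the posttest, as if each unit of pretest predicted exactly one unit of posttest. The actual within-group slope is r × SD(post)/SD(pre), where r is the pre-post correlation. When that slope is not 1, part of the pretest variation stays in the change score as noise. When it is below 1, the group that happens to have the lower pretest mean will also tend to show the larger gain. These are two views of one effect, not two separate faults. Dividing by the pretest SD only rescales the outcome; it does not adjust for pretest.

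What is at stake is efficiency, not bias or false positives. It matters most for the pairwise comparisons. The two theories are separated by specific orderings of the groups (Objectives), and those contrasts carry the Bonferroni penalty. Predictions that groups will be equal also need narrow intervals to be informative.

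**Working it through.** **Inputs from the documents:** four randomised groups; outcome (post − pre)/SD(pre); power .90, effect size .43, alpha .05.

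**Assumed, because the documents do not give them:** r = .5 to .8; q = SD(post)/SD(pre) of 1, 1.25 or 0.8; equal group sizes; .43 read as Cohen's f, standardised by the SD of the change score.

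**1. The plan's power figure.** With no N stated, the .90 cannot be reproduced directly, but the implied N can be solved. For a one-way ANOVA with k = 4 and noncentrality N × f², f = .43 gives power .897 at N = 80 and .901 at N = 81. The implied trial has about 80 participants, and 81 reach .90.

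**2. Error variance.** Set SD(pre) = 1, so the slope is b = rq.

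- Change score: 1 + q² − 2rq
- ANCOVA residual: q²(1 − r²)
- Difference: (1 − rq)² = (1 − b)²

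The difference is never negative and is zero only at b = 1. A slope above 1 loses precision as well. Example with q = 1, r = .5: change variance 1 + 1 − 1 = 1.00; ANCOVA .75; ratio .75. With equal SDs the ratio is (1 + r)/2. These ratios do not depend on N.

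**3. Power and required N.** The effect size becomes f/√(ratio), with one fewer error degree of freedom. Entries are for r = .5/.6/.7/.8.

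| SD(post)/SD(pre) | Variance ratio, ANCOVA to change | ANCOVA power at N = 80 (ANOVA .897) | N for power .90 (ANOVA 81) |
|---|---|---|---|
| 1 | .750/.800/.850/.900 | .966/.954/.942/.928 | 62/66/70/74 |
| 1.25 | .893/.941/.981/1.000 | .930/.915/.903/.897 | 73/77/80/81 |
| 0.8 | .571/.602/.628/.640 | .992/.989/.986/.985 | 49/51/53/54 |

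**4. Pairwise contrasts.** Assume 20 per group, all six pairs Bonferroni-corrected, equal SDs and r = .5 to .8. For a true difference of 1.0 change-score SD, power is .67 with ANOVA and .73–.82 with ANCOVA. For 0.8 SD it is .43 against .49–.59.

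**5. Other reading of .43.** If .43 is Cohen's d with two groups at each extreme, then f = .43/2 = .215 and N is about 311. Power then goes from .900 to .930–.967 (q = 1) or .900–.932 (q = 1.25), much as before.

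**6. Validity check by simulation.** With 20 per group and 4,000 runs per setting, type I error was .049–.055 for the ANOVA and .044–.055 for ANCOVA. Both hold alpha.

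**The case against.** The strongest reply is that nothing here is an error. The planned test is valid, the plan already claims .90 power, and the omnibus gain is about 3 to 7 points with equal SDs and 0 to 3 at an SD ratio of 1.25. That is true, and it is why the point is put as lost efficiency only.

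Several narrower objections also have substance:

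- **Near slope 1 there is no gain.** Besides the degree of freedom, ANCOVA pays for chance imbalance in the covariate, about 1/(80 − 4 − 2) = 1.4% of variance at N = 80. In simulation with an SD ratio of 1.25, ANOVA and ANCOVA power were .898 and .894 at r = .8 (slope 1), and .900 and .901 at r = .7 (slope .875). The possible loss is about .004 in power, against possible gains many times larger.
- **The 0.8 SD ratio has no support in the documents.** The row is an illustrative extreme, and the conclusion does not need it.
- **The Cohen's d reading is not unique.** With two groups at the extremes and two midway, f = .152 and N is about 618. The variance ratios do not change.
- **The starting power is uncertain.** If .43 were Cohen's f in pretest-SD units, N = 80 and SDs equal, ANOVA power would be .90 at r = .5, .99 at r = .7 and about 1.00 at r = .8. Little omnibus power would then be left to gain at the higher correlations, although intervals would still narrow.
- **The study appears to have been run.** The required-N figures therefore only express the size of the loss; they cannot change recruitment.

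**Conclusion.** The concern holds. The analysis of outcome (a) is unbiased and keeps its type I error, but it leaves out a baseline covariate already in hand and so gives up precision whenever the pretest slope is not close to 1. For assumed correlations of .5 to .8, the avoidable share of error variance is 10–25% with equal SDs and 0–11% with a posttest SD 1.25 times the pretest SD. It would be 36–43% only if the posttest SD were 0.8 times the pretest SD. The loss is nil at slope 1, for example r = .8 with ratio 1.25. The variance shares rest on the assumed r and SD ratio alone; the power figures also rest on a back-calculated N and on how .43 is read. This should be changed, but it does not invalidate the planned test.

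**What to change.** Analyse the posttest score, or the standardised change, by ANCOVA with group and the same measure's pretest score as terms, and make the Bonferroni comparisons on the adjusted means. Keeping standardised change as the response preserves the plan's outcome; under randomisation, both analyses estimate the same group differences. Report adjusted contrasts with confidence intervals, together with the pre-post correlation and both SDs, so that readers can see how much the adjustment gained.

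The cost is one degree of freedom and no new data. The plan is written in the past tense and Methods reports an observed pretest-posttest interval. If outcome results are already known, the ANCOVA must be disclosed as added afterwards and shown beside the original ANOVA, not in place of it.

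Optionally, pretest reading span could be added to the Phase 2 mixed model, now described as "an analysis with Training Day and Phase 1 Training Group as the fixed factors". This would sharpen only contrasts in level, such as the prediction under Objectives that Direct Transfer "predicts an early advantage for the ST group relative to the other three groups". A covariate correlating .5 to .7 with level removes .5² to .7², or 25–49%, of the between-person variance in level. With complete days it leaves the day-by-group slopes unchanged, so it does not help the test of learning rate.

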pre- to posttest improvement in RS, but the least improvement in all other span tasks. The DS group (who practiced the lexical decision span (LDS) in Phase 1 and RS in Phase 2) and the DM group (who practiced the category span (CatS) and LDS) in Phase 1 and RS in Phase 2), however, would be expected to show some improvement in the trained tasks according to their collective exposure across the two phases (i.e., DS=DM on RS; DS>DM on LDS; DM>DS on CatS), and less improvement in the untrained tasks, and even less in the episodic memory task (which would represent far transfer). According to the principle of Mutualism, performance is most likely to be enhanced when elements of the task are acquired and then the target task containing those elements is practiced. This situation is embodied in the DM condition in which the individual acquires multiple elements of the WM task that are then practiced in the context of a new task. Thus, the Principle of Mutualism predicts the largest gains from pre- to posttest for the DM group, and to a lesser extent for the DS group, who had less diverse exposure to elements of the WM task relative to the DM group. Because there was no opportunity to practice the untrained WM tasks or episodic memory task, the Principle of Mutualism does not predict improvement in these areas.

Collectively then, Principles of Direct Transfer and of Mutualism make quite different predictions for performance in the successive enrichment paradigm and in pre- to posttest change. Most importantly, the former predicts the reading span in Phase 2 will be acquired the most quickly and show the largest pre- to posttest gains by the ST group, while the latter predicts faster acquisition and largest pre- to posttest gains by the DM and (to a lesser extent) the DS group.

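### For the pairwise comparisons of pre- to posttest change, Holm's step-down should replace single-step Bonferroni, and the stated .9 should not be read as the power of the DM-versus-ST comparison

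*Combined protocol and SAP*

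**What the plan says.** The Statistical Analysis Plan tests standardised pre- to posttest change with a "one-way ANOVA to test differences among the four groups", followed by "post hoc Bonferroni comparisons to correct for the number of" comparisons. It does not say how many comparisons are in the family, and it names no planned contrast.

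The power statement reads: "The design was powered at .9 to detect an effect size of .43 for differences between the groups with an alpha of .05". It gives no sample size, does not say whether .43 is Cohen's f or a two-group d, and mentions no adjusted alpha. A second figure is given for Phase 2: "to detect an effect size of .14 for group differences in change across 10 days".

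The Objectives of the Study Protocol close by stating what most separates the two theories on reading span. Direct Transfer predicts "largest pre- to posttest gains by the ST group, while the latter predicts faster acquisition and largest pre- to posttest gains" in DM and, to a lesser extent, DS. The Design section words the critical tests more broadly, as whether the four groups differ.

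**The concern.** Both theories predict that the groups differ, so a significant omnibus F does not tell them apart. The sign of DM minus ST on reading span gain does. That pair has no status of its own in the SAP. It is one of the post hoc pairs and carries the full Bonferroni penalty, although Holm gives the same error control with at least as much power.

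The only power figure for group differences is .9, and it does not carry over to a pair tested at an adjusted level. If it is taken to do so, a non-significant DM-ST result could be read as evidence that the theories do not differ, when the test had a modest chance of detecting the difference.

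**Working it through.** **Inputs.** From the SAP: four groups, alpha .05, power .9, effect size .43. Assumed: equal allocation, all six pairs in the family (4 × 3 / 2 = 6), two-sided tests with the pooled ANOVA error, and .43 read as omnibus f. N is not in the documents and is back-solved.

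**The plan's own figure.** Omnibus F has 3 and N − 4 df and noncentrality N × f². At N = 80: 80 × .43² = 14.79, critical F(3, 76) = 2.725, power .897. At N = 81 power is .901. So .9 fits N of about 80, or 20 per group. The .14 figure also fits about 80 if the correlation between training days is .5, but that correlation is not stated: N is about 108 at .3 and 48 at .7. It supports N = 80 only weakly.

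**Pairwise power.** With n = 20 per group and 76 df, noncentrality is d × √(n/2) = 3.162 × d. The two-sided critical t is 2.709 at .05/6 = .0083 and 1.992 at .05. Each pattern of means is scaled so that the standard deviation of the four means equals .43 within-group SD, which keeps omnibus power at about .90 throughout. Example for equal steps 0, 1, 2, 3: the SD of the scores is √1.25 = 1.118, one step is .43/1.118 = .385, and DM − ST is two steps, d = .77. Noncentrality is 2.43 and Bonferroni power .40. Holm figures are simulated.

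| Pattern of means | d, DM vs ST (absolute) | Bonferroni, 6 pairs | Holm | Unadjusted .05 |
|---|---|---|---|---|
| PC 0, ST 1, DS 1.5, DM 2 | .58 | .20 | .24 | .44 |
| ST > DS = DM > PC (2, 1, 1, 0) | .61 | .22 | .27 | .48 |
| PC < ST < DS < DM, equal steps | .77 | .40 | .44 | .67 |
| PC = ST < DS = DM | .86 | .51 | .56 | .77 |
| Only DM raised | .99 | .67 | .70 | .87 |
| PC = ST < DS < DM (0, 0, 1, 2) | 1.04 | .71 | .74 | .90 |
| DM and ST at opposite extremes | 1.22 | .87 | .87 | .97 |

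The second row is the ordering that Direct Transfer predicts for reading span in the Objectives. The difference detectable with power .9 at 20 per group is d = 1.27 under Bonferroni and 1.04 at an unadjusted .05.

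**Why Holm cannot lose.** Holm compares the smallest p-value with .05/6, the next with .05/5, and so on, stopping at the first failure. Everything that Bonferroni rejects, Holm rejects. With all groups equal the first step is the same, so the familywise error is the same: .041 in simulation for either method.

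**A separate contrast at .05.** If DM-ST is tested at .05 outside the family and the other five pairs are Holm-adjusted at .05 (first step .05/5 = .01), the simulated familywise error with all groups equal is .082.

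**The other reading of .43.** As a two-group d at an unadjusted .05, power .9 needs 115 per group (460 in total). Bonferroni power for d = .43 is then .73.

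**The case against.** Bonferroni is valid, and choosing Holm over it can look like taste when the gain is 5 points at most. The Design section defines the critical tests as whether the four groups differ, which the omnibus F addresses. Other pairs matter as well: DM versus DS for the diversity aim, and both against PC. For Phase 2 acquisition, Mutualism predicts DM level with ST, so this pair is the sharp test only for pre- to posttest change. All of this stands. It limits the point to the choice of correction, and Holm serves every pair in the family, not only DM-ST.

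Three stronger readings are tempting.

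- A reader might infer that the SAP claims .9 for pairwise tests. It does not. The phrase "for differences between the groups with an alpha of .05" fits the omnibus test, and no pair is mentioned.
- A reader might infer that DM-ST power is always far below .9. That depends on the means. It is .87 when DM and ST are the extremes, although that pattern puts PC above one of the two, contrary to Direct Transfer. N, the metric and the count of six are also inferred.
- A reader might infer that a planned DM-ST contrast at .05 would be a free gain. Much of its extra power comes from the extra alpha shown above. The text is also in the past tense and reports an observed pretest-posttest interval (mean 34.5 days), so a contrast added now could not be presented as prespecified.

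**Conclusion.** The point holds as a modest improvement to the analysis. Single-step Bonferroni gives up power that Holm recovers at the same familywise error. For DM versus ST the recovery is about 0 to 5 percentage points. Under Bonferroni this pair has power of about .20 to .87 across patterns that all have omnibus f = .43, so the .9 does not describe it. Holm does not change that conclusion.

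The power figures rest on about 80 participants in equal groups, .43 as omnibus f, and six pairs, none of which the documents state. Under the two-group reading of .43, power for the pair is .73, still short of .9. Holm's advantage over Bonferroni rests on none of these assumptions.

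**What to change.** Replace single-step Bonferroni with the Holm step-down for the pairwise comparisons of pre- to posttest change. Where the power is reported, say that .9 refers to the omnibus test.

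The cost is a change of wording and a different adjustment of the same p-values; no further data are needed. The one statistical drawback is that simultaneous confidence intervals matching Holm are less simple than Bonferroni's. Because the text was written after data collection, the switch should be disclosed, and Bonferroni-adjusted p-values can be shown alongside.

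If the sponsor also wants DM-ST to have its own status, it needs either a gate (the other pairs are tested only after it succeeds) or its own share of the .05, and it should be labelled as added after the data were collected.

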## ***Study Protocol***

**Objectives.** While an intellectually active and socially integrated lifestyle shows promise for promoting cognitive resilience with aging, the mechanisms underlying any such effects are not well understood (Stine-Morrow et al., 2014, 2021; Stine-Morrow & Manavbasi, 2022). The aim of the current project was to test the implications of the “Mutualism” hypothesis (Savi et al., 2019; van der Maas et al., 2006; van der Maas et al., 2017), which suggests that intellectual function emerges out of the reciprocal influence of growth in abilities as they are exercised in the ecology of everyday life. Such a view stands in contrast to the Principle of Direct Transfer (Thorndike, 1906) in suggesting that improvement in one component will enhance the *modifiability* of a related component. In other words, while conventional conceptualizations of transfer imply immediate generalization, mutualism assumes that practice in the novel skill is required for benefits to be manifest. An additional aim was to test the idea that mutualistic effects will be enhanced by more diverse training in related skills, relative to single-component training (Brown et al., 2014; Schmidt & Bjork, 1992).

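### Phase 2 acquisition: the plan names only comparisons with PC and writes no Day-by-Group term, so the ST versus DM/DS and DM versus DS predictions have no planned test or interval

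*Combined protocol and SAP*

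**What the plan says.** The Statistical Analysis Plan has two primary outcomes. Pre- to posttest change gets a one-way ANOVA with Bonferroni post hoc comparisons among the four groups. Phase 2 acquisition gets a linear mixed model with a by-subject random intercept, and the comparisons are described in one sentence: "The PC Group was set as reference in comparisons with other groups in an analysis with Training Day and Phase 1 Training Group", both as fixed factors. No Day-by-Group term is written, and the plan does not say whether Day is linear or categorical. It does describe acquisition as change over the ten practice days and gives a power figure for group differences in that change. It states that this model carries no multiplicity correction.

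The Study Protocol, under Objectives, sets out the predictions. Direct Transfer "predicts an early advantage for the ST group relative to the other three groups that would be sustained through acquisition". For the remaining two trained groups the same sentence adds: "as well as some advantage for the two other WM training groups, the DM and DS conditions, relative to the PC condition". Mutualism "predicts accelerated acquisition for the DS, and especially the DM, conditions, relative to the PC condition, on par with the ST condition", and it holds that "any advantage of the DS and DM conditions would not be immediately apparent but only emerge with practice". The closing summary, on the difference it treats as most important, says "the former predicts the reading span in Phase 2 will be acquired the most quickly" by ST, while "the latter predicts faster acquisition and largest pre- to posttest gains by the DM and (to a lesser extent) the DS group". A separate aim is whether "mutualistic effects will be enhanced by more diverse training in related skills, relative to single-component training". Under Design, one of the two critical tests is whether the four groups differ in Phase 2 training gains.

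**The concern.** There are two layers. First, with only the two listed factors the model cannot express the outcome it is meant to analyse: acquisition rate by group needs an interaction. Second, even with the interaction, the named contrasts all share PC. Objectives puts ST, DS and DM ahead of PC under both theories, so PC contrasts can separate the theories only through the time course. The ranking of ST against DM and DS, and the value of diverse over single training, concern pairs that do not include PC. If one of these groups differs significantly from PC and another does not, that is not a test of the difference between them.

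At stake is one of the trial's two critical tests. Conclusions about ranking or diversity would rest on informal comparison of PC contrasts, or on contrasts chosen after the learning curves had been seen.

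**Working it through.** **1. Predictions against named comparisons.**

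| Prediction (Objectives) | Pairs needed | Named in the plan |
|---|---|---|
| Direct Transfer: ST ahead of the other three | ST–PC, ST–DM, ST–DS | ST–PC only |
| Both theories: DM and DS ahead of PC | DM–PC, DS–PC | both |
| Mutualism: DS/DM advantage grows with practice | DM–PC, DS–PC, by Day | pairs named, interaction not written |
| Mutualism: DS and DM level with ST | DM–ST, DS–ST | neither |
| Summary: ST quickest, or DM then DS quickest | DM–ST, DS–ST, DM–DS | none |
| Diversity aim | DM–DS | no |

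Three of six pairs are named. The Bonferroni comparisons cover the other three for pre- to posttest change only.

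**2. What the listed terms can estimate.** With Day linear, Day + Group gives one common slope and three constant offsets from PC. Day × Group adds three slope differences from PC. An illustrative fit to made-up data (21 per group) shows this: the first model returned a single slope of 0.135; the second returned slope differences from PC of 0.112 (DM), 0.064 (DS) and 0.011 (ST). The slope contrasts ST–DM, ST–DS and DM–DS each had a standard error of 0.0237, the same as each PC contrast.

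**3. The plan's power figure.** Power of .9 cannot be reproduced, because neither N nor the effect-size metric is given. Two readings of .43 are possible:
- As f (one-way ANOVA, four groups, alpha .05): power is .897 at 20 per group and .913 at 21.
- As d (two groups, two-sided .05): n = 2(1.960 + 1.282)²/.43² = 113.7, so 114 per group, or 115 with the t distribution.

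The second figure, .14, read as f for the interaction with an assumed correlation of .5, needs N = 77. That agrees with the f reading of .43 (N = 81) but does not confirm it.

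**4. Multiplicity.** Three added pairs on level and change make 6 contrasts; all six pairs make 12. Normal quantiles are 2.638 at .05/6 and 2.865 at .05/12, against 1.960. The ratios are 1.35 and 1.46.

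**5. Precision of a difference in Day 1 to Day 10 change.** Assumed: daily-score SD 1, between-person share (ICC) .5 to .8, random intercept only, ten equally spaced days (sum of squares 82.5), Day linear.

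SE = 9 × √[2(1 − ICC)/(82.5n)]

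Multipliers are t quantiles on the within-person degrees of freedom: about 2.645 and 2.874 for the f reading, 2.640 and 2.867 for the d reading.

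| Reading of .43 | n per group | SE | Half-width at .05/6 | Half-width at .05/12 |
|---|---|---|---|---|
| f | 20–21 | .137–.222 | 0.36–0.59 | 0.39–0.64 |
| d | 114–115 | .058–.093 | 0.15–0.25 | 0.17–0.27 |

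Under the f reading, three variants at .05/6:
- Categorical Day: SE = √[4(1 − ICC)/n] = .195 to .316; half-width 0.52 to 0.84.
- Day 1 level, linear Day: SE = √{(2/n)[ICC + (1 − ICC)(.1 + 20.25/82.5)]} = .253 to .295. With a t multiplier of about 2.71 (76–80 df), the half-width is 0.69 to 0.80.
- True change varying between people with SD 0.5 (assumed): SE = √{(2/n)[81(1 − ICC)/82.5 + .25]} = .206 to .272; with the same 2.71, half-width 0.56 to 0.74.

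**The case against.** The strongest reply is that choosing PC as reference is only coding. Every pair is estimable from the same fit, and point differences follow by subtracting PC coefficients. That stands: the plan neither excludes these contrasts nor leaves them without an estimate. Subtraction does not supply the standard error, which needs the covariance of the coefficients, and the plan commits to no interval or test.

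A second reply is that the contrast with PC over time is the one Objectives calls critical. That stands on condition that the interaction is fitted. Two opposite inferences are tempting here. One is that the PC comparisons, as written, already address the time course; the listed terms do not establish that. The other is that the interaction was never intended or fitted; the wording about change over the ten days, and the power statement for group differences in change, point the other way.

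A reader might also infer that the study is too small for the added contrasts to be useful. The documents do not support that: the wide intervals follow from reading .43 as f, and the d reading more than halves them. Finally, leaving this model uncorrected is the plan's declared choice, so the added interval width comes from the adjustment suggested here, not from the contrasts themselves.

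**Conclusion.** The point holds as a specification gap on a primary outcome and should be fixed. Two things are certain from the text: no Day-by-Group term is written, and no test or interval is planned for ST–DM, ST–DS or DM–DS. Neither depends on any assumption. It is not shown that the analysis performed was wrong, nor that the trial cannot separate the theories.

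The precision figures are conditional on the assumed variance components and on the reading of .43. Under the f reading the adjusted contrasts could well be inconclusive; under the d reading they would be considerably sharper.

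**What to change.** - Write the Day-by-Group interaction and state how Day is coded, so that initial level and change are defined quantities.
- From the same fit, report DM–ST, DS–ST and DM–DS on initial level and on change (slope if Day is linear, Day 1 to Day 10 difference if categorical), with confidence intervals. Keep the PC contrasts for the time-course prediction, and rest ranking and diversity conclusions on the added ones.
- State one multiplicity rule for all the model's contrasts, or say why the PC contrasts stay uncorrected while the added ones are adjusted.
- Say whether parity with ST under Mutualism refers to level and faster acquisition to rate; both can hold. Do not read a non-significant difference from ST as parity; report the interval.
- State N and the metric of .43.
- The Methods and the plan are in the past tense, and Methods reports a group comparison of the test interval. If outcome data have been seen, label the contrasts as added later.

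The cost is a few lines of code and plan wording, with no extra participants. With equal groups, an added contrast is as precise as a PC contrast before adjustment. Bonferroni adjustment widens intervals by about 35% if only the six added contrasts are adjusted, or 46% if one rule covers all twelve. Some contrasts may be inconclusive, and the report should say so.
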